Project Title: Neurobehavioral Substrates of Propranolol's Effects on Drug Cue Reactivity

NCT #: NCT03309943

Document Date: 11/11/2019

We propose to obtain consent from a total of 75 smokers in order to identify 40 who meet all inclusion and exclusion criteria and provide usable data sets. Participants will complete an initial screening either online or over the phone. In both cases, the study will be described in detail and preliminary participant characteristics will be assessed (e.g. age, number of cigarettes per day, use of exclusionary medications or medical conditions that would preclude participation). Online screenings will be administered via Duke REDCap questionnaires. Participants who complete the online screen will also be contacted by phone to confirm information and provide additional study information. Those participants who appear to meet criteria for participation will be invited to our offices for an informed consent and screening visit. Identifying information from the phone screen for participants who do not meet inclusion criteria will be kept until recruitment for this study is completed and stored on a secure department server. See Waiver of Consent and HIPAA authorization. Participants or potential participants will be provided with a copy of the drug insert upon request - either by email/postal mail in advance of participation or at their screening visit.

Screening Session

Volunteers who meet initial eligibility criteria (determined by online/phone screening) will be asked to attend an in-person screening approximately 2-3 hours in length. The PI or other study staff will give a ~10 minute presentation describing details of the study procedures and risks. They will be provided with a consent document to review and given the opportunity to ask questions. They will then obtain informed consent.

Afterwards, participants will:

- Provide breath samples for expired breath carbon monoxide (CO) level analysis using a CO meter. This is a reliable and valid measure of recent smoking.
- Provide a breath sample for analysis of breath alcohol level using an AlcoSensor breathalyzer device. Participants with levels $> .000$ will be offered one opportunity to reschedule their visit – any further positive readings will result in exclusion.
- Urine samples will be obtained to screen for pregnancy (HCG) among female participants and illicit drug use among all participants.
- Established questionnaires will be used to assess nicotine dependence (Fagerström Test for Nicotine Dependence) and quit motivation (Contemplation ladder). A detailed smoking history will also be obtained.
- Additional questionnaires will be used to assess other potential moderators and variables of interest for exploratory analysis
- The MINI International Neuropsychiatric Interview will be conducted by the PI or other staff working under his supervision in order to screen for exclusionary psychopathology.
- Participants will undergo a full physical exam conducted by the study physician ([name]) to ensure safety of propranolol administration. This will include blood pressure readings and EKG. A blood sample will be drawn and submitted for analysis (CBC, basic metabolic panel and serum pregnancy [females]) and reviewed once available (prior to drug administration). Depending on scheduling and physician/psychologist availability, participants will also have the option of completing the physical exam and clinical interview at the training visit or camera return visit. These will always occur prior to randomization/drug administration.
- Complete a visual acuity exam

Certain components of the procedure (e.g. MINI, cognitive tests) may be audio recorded. Failure to meet requirements for the study will result in dismissal. Sexually active females must agree to use contraception during the course of the study and notify study staff if they become pregnant during the course of the study. Per standard procedures at the Brain Imaging and Analysis Center, an additional pregnancy test will occur at these sessions.

Training Session

Participants who did not complete a medical exam at the baseline visit will do so at this visit. In addition, they will be exposed to a “mock” MRI scanner and asked to complete an abbreviated picture viewing task so that they can experience the scanner environment and ensure they are comfortable completing MRI sessions.

Eligible participants will be trained in the picture-taking procedures, provided a camera if they do not own a suitable one and scheduled to return in approximately one week. They will be asked to take > 5 photographs of smoking and non-smoking environments as identified during interviews.

Camera Return Session

Participants will return the camera they were provided. Images will be downloaded and reviewed for appropriateness. If necessary, they will be given additional time to obtain appropriate images. If images are deemed appropriate, the participant will be scheduled for an MRI session. In addition, participants will complete a brief “Environment Go-NoGo task.” This is a modified version of the standard Go-NoGo task. Stimuli (letters, numbers or symbols) will be embedded in images consisting of smoking (e.g. bus stop) or non-smoking (e.g. church) environments. Participants will view blocks of these stimuli be instructed to identify the presence of a particular stimulus by button press. .

fMRI Session

Participants will be required to be 24 hours abstinent at the time of the scan as indicated by a breath CO level < 8 ppm. Participants will also be tested for breath alcohol and must record a BrAC of < 0.001. Participants who do not meet the CO level may be provided one opportunity to reschedule at the discretion of the PI or study staff. Participants who are unable to attain the required CO level will be withdrawn. Participants will be instructed to eat 1 hour prior to their appointment in an effort to standardize drug absorption. Research staff will meet participants at the scanning facility. Drug will be stored in a secure closet in our laboratory and walked over to the hospital for administration during the scanning session. CO will be collected upon participant arrival. Afterwards, participants will be randomly assigned to propranolol (40 mg) or placebo conditions. These will be administered 1.5 hours prior to scanning. Heart rate and BP will be monitored every 45 minutes during the intervening period. Self-report assessments of craving (Questionnaire on Smoking Urges – Brief) and nicotine withdrawal (Minnesota Nicotine Withdrawal Scale), among other measures, will be obtained immediately prior to drug administration and again immediately prior to scanning. During the scan, participants will be positioned in a 3T MRI scanner and completing a resting scan, anatomical scan and several function runs during which they will view images of the environments they photographed, as well as standard smoking/non-smoking environments and proximal smoking/neutral cues. Heart rate and respiration will be monitored during resting tasks. Respiration will be monitored during all tasks.

Laboratory Session

Participants will attend a final laboratory session. They will be required to be 6 hours abstinent at the time of the session as indicated by a 40% reduction in breath CO from the value obtained at the screening session.

Participants will also be tested for breath alcohol and must record a BrAC of < 0.001. As above, participants who do not meet the CO level may be provided one opportunity to reschedule at the discretion of the PI or study staff. Participants who are unable to attain the required CO level will be withdrawn. Next, they will repeat the previously administered craving/withdrawal measures. As with the MRI session, participants will be instructed to eat 1 hour prior to their appointment in an effort to standardize drug absorption. A second dose of propranolol or placebo will be administered 1.5 hours before the cue exposure task. As above, heart rate and BP will be monitored during the intervening period and self-report assessments of craving and withdrawal will be obtained immediately prior to beginning the task. The task will consist of an initial 2-minute cue exposure period, followed by an additional craving assessment. Next, participants will view cues for an additional 12 minutes during which they will have *ad libitum* access to their cigarettes and are informed they may smoke freely. Participant behavior will be video recorded during this period for later coding by video. After the *ad lib* smoking period, participants will complete an additional set of measures, as well as an additional CO assessment. At the conclusion of this session, participants will meet with the PI or staff working under his

supervision. They will be provided with the smoking behavior report, psychoeducation about smoking behavior and the importance of cessation, and a list of referrals. In addition, they will be provided with a stack of study recruitment materials and encouraged to distribute them to family and friends who smoke as typical of a snowball sampling approach. However, per Duke IRB policy, no incentives will be offered for distributing these materials.

Statistical Analysis Plan

Analyses will examine the effects of propranolol: (1) BOLD activation and connectivity in response to smoking cues; (2) Smoking urge in response to smoking cues during the MRI task; (3) Smoking urge in response to personal smoking environment cues during the laboratory task; and (4) Smoking behavior during the laboratory smoking task.

Primarily analyses of BOLD activation results will utilize and ROI-based approach. Percent signal change in response to all cue types will be extracted from the hippocampus (both posterior and anterior), amygdala, medial prefrontal cortex and anterior insula. Extracted values will then be examined using SPSS mixed models, utilizing repeated statements in lieu of random effects (analogous to repeated measures ANOVA). A compound symmetry covariance structure will be specified. Analyses will examine the effects of drug condition on cue reactivity. For BOLD Activation, our primary outcome will be the overall smoking cue reactivity effects (i.e. collapsing across image type – proximal, standard environment, personal environment) although planned contrasts will break these down by individual image types to clarify effects. In addition, we will use a psychophysiological interaction approach to extract indices of brain connectivity while viewing smoking-related images. We anticipate using a hippocampus seed based on pre-clinical findings, but a final determination will be based on the pattern of activation observed in the present study. Any baseline group differences will be adjusted for in these analyses. Connectivity between the seed region and other relevant brain regions (same as above) will also be examined. An identical approach will be used to examining smoking urge during the MRI task.

Smoking urge and behavioral outcomes for the laboratory task will be analyzed using similar procedures. First, video data will be coded by two independent raters. Substantive disagreements will be resolved through discussion, the average value will be taken when minor disparities are present. For self-reported urge, analyses will examine drug effects on post-cue-presentation urge ratings (again, adjusting for any baseline group differences, as well as pre-cue-presentation urge rating). Analysis of behavioral outcomes will follow a similar approach – although a variety of indices of smoking behavior will be computed our primary focus will be on the total number of puffs taken across the *ad lib* smoking period (aggregated across cigarettes when relevant).

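### If all cue cells enter one compound-symmetry model, the standard error of the primary BOLD drug-by-cue test can be too small or too large, and the plan does not say whether image types are averaged first

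*Combined protocol and SAP*

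**What the plan says.** The BOLD paragraph of the Statistical Analysis Plan starts from cell-level data: "Percent signal change in response to all cue types will be extracted" from each region of interest. These values go into SPSS mixed models "utilizing repeated statements in lieu of random effects (analogous to repeated measures ANOVA"), and then: "A compound symmetry covariance structure will be specified". For BOLD, "our primary outcome will be the overall smoking cue reactivity effects", collapsed over proximal, standard-environment and personal-environment images, while "planned contrasts will break these down by individual image types to clarify effects". For urge in the scanner: "An identical approach will be used to examining smoking urge during the MRI task".

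The number of cells is not stated. It can be inferred. Under Training Session, participants take "photographs of smoking and non-smoking environments as identified during interviews". Under fMRI Session they view these, "as well as standard smoking/non-smoking environments and proximal smoking/neutral cues". That is three image types, each with a smoking and a control version, so six cells per participant and region.

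The plan does not say whether collapsing means averaging before the model is fitted or taking a marginal contrast from a model that holds all six cells. It names no alternative covariance, participant-by-cue term, robust standard error or covariance check.

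**The concern.** Compound symmetry assumes one variance and one correlation for every pair of cells. Over six cells, two plausible features of cue-reactivity data break it: participants may differ in how strongly they respond to smoking versus control images, and two images of the same type may be more alike than images of different types. A six-cell model without random effects puts both into a single residual and uses it to test every within-person contrast.

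The comparison with repeated measures ANOVA does not settle the matter. A factorial repeated measures ANOVA tests drug-by-cue against its own participant-by-cue error; a compound-symmetry model over all cells uses the pooled one.

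At stake are the p-values and confidence intervals of the primary BOLD outcome and of its planned contrasts. With complete data the point estimate is the same either way, so leaving the choice open allows two different p-values from one data set.

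**Working it through.** **Inputs from the documents.** 40 usable participants (opening paragraph of the protocol); two randomised arms (fMRI Session); compound symmetry without random effects (Statistical Analysis Plan). The plan gives no power calculation, alpha or variance for this test, so there is no figure to reproduce.

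**Assumptions.** 20 per arm, two-sided 5%, regions modelled separately, complete data, six cells. Each value is a participant level, plus a participant-specific reactivity times +0.5 (smoking) or −0.5 (control), plus a participant-specific effect shared by the two cells of an image type, plus residual. The variances are B (reactivity), G (image type) and E (residual, set to 1).

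**Degrees of freedom.** Pooled within-person error: 5 × (40 − 2) = 190. Participant-by-cue error: 40 − 2 = 38.

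**Expected pooled residual.** Reactivity contributes 6 × 0.25 × B = 1.5B to the within-person sum of squares, image type 2 × 2 × G = 4G, and residual 5E. Dividing by 5 gives R = 0.3B + 0.8G + E.

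**Per-participant variance of each contrast.**

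- Primary (mean of three smoking cells minus mean of three control cells): model (2/3)R, truth B + (2/3)E. They are equal when 0.2B + (1.6/3)G = B, that is G = 1.5B.
- Single image type (one smoking cell minus one control cell): model 2R, truth B + 2E. They are equal when 0.6B + 1.6G = B, that is G = 0.25B.

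Both conditions hold together only if B = G = 0. For example, at B = 1, G = 0, R = 1.3. The primary SE ratio (model/true) is √(0.867/1.667) = 0.72 and the single-type ratio is √(2.6/3) = 0.93.

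**Simulated type I error, six-cell model (40,000 null trials per scenario).**

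| B, G | R | SE ratio, primary | SE ratio, single type | Type I, primary | Type I, single type |
|---|---|---|---|---|---|
| 0.5, 0 | 1.15 | 0.81 | 0.96 | 11% | 5.9% |
| 1, 0 | 1.30 | 0.72 | 0.93 | 16% | 6.8% |
| 2, 0 | 1.60 | 0.63 | 0.89 | 21% | 7.8% |
| 1, 0.25 | 1.50 | 0.77 | 1.00 | 12.8% | 5.0% |
| 1, 1 | 2.10 | 0.92 | 1.18 | 7.2% | 2.1% |
| 1, 1.5 | 2.50 | 1.00 | 1.29 | 5.0% | 1.2% |
| 0, 1 | 1.80 | 1.34 | 1.34 | 0.9% | 0.9% |

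Further primary-test results: (0.5, 0.5) 6.7%, (2, 2) 8.1%, (0.5, 1) 3.9%. With 16 and 24 per arm, the scenarios that were repeated gave nearly the same results.

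**Comparison method.** A two-sample t-test on each participant's difference score gave 4.8% to 5.2% in every scenario for both tests. Compound symmetry fitted to two averaged cells matched it for the primary test. In one simulated data set with an estimated effect of 0.112, the standard error was 0.322 from the six-cell fit, and 0.481 from both the two-cell fit and the difference score.

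**Power.** At (0, 1), with a true effect of 0.742 (80,000 trials), power was 59% in the six-cell model and 80% with the difference score. With compound symmetry exactly true it was 81.6% and 80.0%.

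**The case against.** The plan never says that six cells enter one model. Averaging first is a natural reading of collapsing, and the primary test is then valid. A third reading is also open: smoking-minus-control reactivity could be computed for each image type and the three differences modelled. The drug main effect is then tested on participant means with 38 df. Simulation of that version under the same data model kept both tests near 5% (4.6% to 5.4%). The variance components are assumed, and the largest error rates set the image-type variance to zero. With small equal variances the primary test is nearly correct: 5.4% at (0.1, 0.1) and 5.8% at (0.25, 0.25). The two balance points belong to the two-component model chosen here.

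All of this stands as a limit on how certain the harm is. It does not remove the problem. The text extracts values for all cue types and puts those values into a repeated-measures model that must also yield image-type contrasts. One multi-cell model is the most natural reading of that, although the text does not prove it. Nothing in the documents adds an averaging step, a differencing step or a separate error term.

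**Conclusion.** The concern holds, conditionally on the six-cell reading. Under that reading, the error rate of the primary BOLD test depends on a covariance assumption that nobody is set to check. Across the assumed variances it ran from 0.9% to 21%. The overall effect and its breakdown can also be wrong in opposite directions in the same model: at (1, 1) the primary test rejects too often (7.2%) and the single-type contrast too rarely (2.1%). The size and direction in this trial cannot be known from the documents. If values are averaged over image type first, the primary test is sound. Scanner urge is affected only if it is rated per cue type, which the documents do not state. This should be settled before analysis; confidence is medium because the harm depends on an unstated step.

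**What to change.** State in the Statistical Analysis Plan that, for each participant and region, the primary variable is the mean of the smoking cells minus the mean of the control cells. Compare arms on it by a two-sample test or ANCOVA with about 38 df, one fewer per covariate. Use the same difference within each image type for the planned contrasts, and for scanner urge if it is rated per cue type. This is valid whichever reading was intended. If averaging first was always meant, the sentence only records it.

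Alternatively, keep the SPSS mixed model with an unstructured covariance over the cells and small-sample degrees of freedom. This also keeps participants who lack a cell, but it estimates 6 × 7 / 2 = 21 covariance parameters from about 40 participants.

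The cost is one or two sentences and no new data. If compound symmetry is exactly true, the difference score loses about 1.6 points of power (81.6% to 80.0%). It also needs a stated rule for a participant with an unusable cell.

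### Covariates are chosen by chance baseline imbalance, with no variables, test or threshold stated; name them in advance and use them whatever the balance

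*Combined protocol and SAP*

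**What the plan says.** All the relevant text is in the Statistical Analysis Plan section.

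- **Imaging.** The BOLD and connectivity paragraph says "Any baseline group differences will be adjusted for in these analyses". The next sentence stays with connectivity: "Connectivity between the seed region and other relevant brain regions (same as above) will also be examined".
- **MRI urge.** "An identical approach will be used to examining smoking urge during the MRI task". No covariate is named.
- **Laboratory urge.** The post-cue rating is analysed "adjusting for any baseline group differences, as well as pre-cue-presentation urge rating". The pre-cue rating is the only covariate that the plan names and uses whatever the balance.
- **Puffs and other smoking behaviour.** "Analysis of behavioral outcomes will follow a similar approach". No covariate is named in that sentence.

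The documents do not say which variables are compared, by what test, against what threshold, or who decides. Many candidates are collected. The online or phone screen records cigarettes per day. The Screening Session adds dependence, quit motivation, a smoking history and an unspecified number of further questionnaires. The fMRI Session adds craving and withdrawal scores taken just before dosing.

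**The concern.** Arms formed by randomisation differ at baseline only by chance, so an observed difference says nothing about whether a variable is worth adjusting for. A covariate earns its place by predicting the outcome. A rule that waits for imbalance leaves a strong predictor out of most trials and lets an irrelevant variable in when it happens to differ.

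Two things are at stake. The trial plans for 40 usable data sets, so precision is scarce, and a predictive baseline measure used every time could add some at almost no cost. The rule also cannot be carried out as written: two analysts following the same sentence can fit different models to the same data.

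**Working it through.** **Inputs.** The 40 usable data sets come from the recruitment paragraph. Allocation ratio, alpha, effect size and SD are not stated, so the plan has no figure of its own to reproduce. Assumed here: 20 per arm, two-sided 0.05, effect 0.8 SD, normal outcomes, and covariate-outcome correlation r from 0 to 0.7.

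**1. How often the rule fires by chance.** With k independent variables and threshold a, the chance of at least one flagged difference is 1 − (1 − a)^k. For k = 5, 10, 20:

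- a = 0.05: 23%, 40%, 64%
- a = 0.20: 67%, 89%, 99%

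The chance that the two thresholds select different covariate sets is the chance that some p-value lies between 0.05 and 0.20, which is 1 − 0.85^k: 15% for k = 1, 39% for k = 3, 56% for k = 5 and 80% for k = 10. Correlated candidates would lower these figures.

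**2. What a p<0.05 test can see.** The smallest flagged difference at 20 per arm is t(0.975, 38) × √(2/20) = 2.024 × 0.316 = 0.64 SD. Smaller imbalances in a strong predictor go unadjusted.

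**3. Precision for a between-arm outcome.** The unadjusted standard error is √(2/20) = 0.316 SD. Fixed adjustment multiplies it by about √(1 − r²): 0.302 at r = 0.3, 0.274 at r = 0.5 and 0.226 at r = 0.7. With one candidate, a p<0.05 trigger adjusts in about 1 trial in 20, so almost none of this is realised. Simulated power (40,000 trials per setting, ordinary least squares):

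| r | Unadjusted | Trigger p<0.05 | Trigger p<0.20 | Always adjusted |
|---|---|---|---|---|
| 0 | 69% | 69% | 68% | 68% |
| 0.3 | 69% | 69% | 69% | 72% |
| 0.5 | 70% | 70% | 72% | 80% |
| 0.7 | 69% | 71% | 76% | 93% |

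With ten independent candidates of which one is predictive (20,000 trials), imbalance-driven adjustment gave 63–69% across thresholds of 0.05 to 0.20 and r of 0.3 to 0.7. That is no better than the 69–70% without adjustment.

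**4. Drug-by-cue contrast (MRI urge).** A participant-level main effect does not change a balanced within-person contrast, so a covariate-by-cue term is needed. The assumed effect is 0.8 SD of the cue difference, with within-person correlation 0.6. If craving relates equally to both cue types, power is 68% with the term and 69–70% without it. If craving correlates 0.2, 0.3 or 0.5 with the cue difference itself, power is 70, 72 or 80% with the term and 69–70% without.

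**5. Type I error.** A preset p<0.05 trigger with one candidate gives 5.1, 4.6, 4.4 and 3.7% at r = 0, 0.3, 0.5 and 0.7. If the analyst keeps the smallest p-value over the open choices, it is 5.7–6.3% with two or three related candidates (variables and threshold both free). It is 6.5–7.2% with ten independent candidates (unadjusted, or thresholds 0.05, 0.10 and 0.20).

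**The case against.** The strongest defence is that this is a small mechanistic study, adjusting for observed imbalance is customary, and the promised gain may not exist. Much of that stands. The primary BOLD outcome concerns cue reactivity ("Analyses will examine the effects of drug condition on cue reactivity"), for which no power gain is claimed. For puffs the gain is only about 3 points at r = 0.3; the large gains need r of 0.5 to 0.7, and the documents give no value. What does not stand is the appeal to custom, which supplies neither the missing variables nor the threshold. The plan already names a fixed covariate for laboratory urge, so naming one elsewhere is feasible.

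Four stronger readings are tempting but not supported.

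- *The rule inflates type I error.* A trigger fixed in advance is slightly conservative. Inflation appears only if the open choices are used selectively, and is then modest. Nothing in the documents says they would be.
- *MRI urge has no stated adjustment.* The identical-approach sentence follows the rule closely, and the laboratory clause introduces the rule with the word *again*. Both indicate that it already covers the earlier analyses.
- *No covariate is prespecified, and puffs certainly have none.* Laboratory urge has the pre-cue rating, and the similar-approach wording may carry that rating over to puffs.
- *Adjusting for the pre-cue rating isolates the cue-induced part of the drug effect.* The stated aim is "Smoking urge in response to personal smoking environment cues during the laboratory task", and the Laboratory Session says "A second dose of propranolol or placebo will be administered 1.5 hours before the cue exposure task", with craving rated again just before the task. The pre-cue rating therefore appears to follow the dose. Adjustment then gives a conditional effect. With an assumed total of 0.80 SD, half of it present before cues, and slope 0.7, the estimate is 0.80 − 0.7 × 0.40 = 0.52 SD, while the cue-induced part is 0.40 SD. With a quarter present before cues, it is 0.80 − 0.7 × 0.20 = 0.66 against 0.60 SD. This is no reason to remove the covariate.

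**Conclusion.** The concern holds as a matter of precision and prespecification. The adjustment rule is undefined, and imbalance is the wrong criterion for choosing covariates. For a between-arm outcome such as puffs, always using one named predictor instead of a p<0.05 trigger changes power by about −1, +3, +10 and +22 points at r = 0, 0.3, 0.5 and 0.7. These figures rest on the assumed 20 per arm, 0.8 SD, two-sided 0.05 and normal outcomes, and r is unknown. For BOLD and connectivity the benefit is a model fixed in advance. The same is true of MRI urge read as a drug-by-cue contrast, unless the covariate predicts the cue difference itself. The defect does not invalidate the trial, but it should be corrected.

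**What to change.** Delete the baseline-difference trigger in both places. Name the covariates for each outcome and use them whatever balance is observed:

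- **Puffs:** one screening smoking measure, cigarettes per day. State whether the pre-cue urge rating also applies.
- **MRI urge:** the QSU-Brief taken before dosing in the fMRI session, with a covariate-by-cue term if the target is the drug-by-cue contrast.
- **BOLD and connectivity:** no covariates in the primary model.
- **Laboratory urge:** keep the pre-cue rating already specified.

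Any adjustment prompted by observed imbalance becomes a labelled sensitivity analysis.

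The change is to wording only, since every measure is already collected. It uses one or two degrees of freedom per model and costs about 1 point of power if the covariate turns out not to be predictive.
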